Dupclay et al 2012	Single dose blister packaging	63% (26%)	76 (25%)	Hypertension

Statistical Analysis

Mean medication adherence was calculated as the proportion of days covered (PDC) for hypoglycemic medications. The change in medication adherence (pre-intervention PDC subtracted from the post-intervention PDC = change score) will be compared using unpaired t tests. For the primary endpoint, analyses will be performed according to the intention-to-treat principle. Change in mean medication adherence between the 2 study groups (usual care and intervention) will be compared by using a t test for independent groups. Patients who do not complete the randomized trial (because of death or withdrawal) will be analyzed by the imputation method of last observation carried forward, using the medication adherence level of the time available. A similar methodology will be used for the secondary (exploratory) endpoints of diabetes control and re-admission rate.

Exploratory analysis: To control for baseline differences between study groups, a multivariable analysis will be performed for the randomized trial primary end point. The dependent variable for this analysis will also be the change score (the change in medication adherence between pre-treatment and post-treatment). The independent variables will be those baseline characteristics that had between group comparisons with $P < .20$, in addition to the randomized trial group assignment, clinic site and the baseline (run-in phase) medication adherence. The criteria for statistical significance for the primary outcomes will be a two-sided $p < 0.05$. The above statistical methodology is based on the approach used by Lee et al., JAMA 2006.

Target Population

We will recruit adults with independence Blue Cross medical and pharmacy coverage, Type II DM, HbA1C ≥ 7.5 , and a current medication regimen that only includes oral therapy. If patients are eligible for participation an initial meeting will be arranged with a trained research coordinator to enroll them in the study. This meeting will occur either in the clinic or in the patient's home in the case the patient is unable to commute to the clinic. Eligible participants will be randomized to either treatment or control arms with a target allocation ratio of 1:1. With the estimated sample size (75 treatment, 75 control) we have 80% power to detect up to a 15% change in medication adherence. This assumes a dropout rate of 15% percent and a standard deviation of 30%.

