 - a. "This is the last reminder to take your [morning, afternoon, and nightly] medication! There is no need to respond to this notification –The Penn Medicine Team"
4. All patients will receive an automated phone call reminder to refill their medication tray 10 days prior to their refill date. Patients with cell phones will also receive a text message reminder.
 - a. "Please be sure to refill your medications by calling [contact] during regular business hours"-The Penn Team"

Patients will have the option to turn on or off the pillbox's light and sound feature. The rationale for introducing the "P" or "2" option into the reminder system is to better understand if reminders before a medication dose are constructive when compared to simply reminding a patient after they have already forgotten their dose. Notifications after a dose is due may reduce reminder fatigue as the patient is given the opportunity to remember their dose from memory alone.

Research Coordinator Outreach

In addition to patient facing software through which patients can view their medication adherence and make changes to notification schedules, TowerView has designed a care coordinator/nurse dashboard. Using this dashboard the research coordinator is able to view the adherence of all patients using the connected pillbox. Patients who are continuously nonadherent- 3 consecutive missed doses or 5 doses out of 12 over a 4-day period receive targeted outreach from the research coordinator. This call is designed to explore the etiology of patient nonadherence as well as potentially change patient behavior using motivational interviewing techniques.

Primary Endpoint:

- Medication adherence as defined by PDC rates for both the treatment and control group

Secondary (Exploratory) Endpoints:

- Time to treatment discontinuation (rate of medication persistence)
- Glycated hemoglobin (HbA1C), which is generally collected every three months as part of routine clinical care for diabetic patients with HbA1C over 7.5
- Blood pressure
- Body Mass Index (BMI)
- Emergency Room (ER) visits
- Absolute cost
- Overall healthcare utilization
- Patient Satisfaction with research treatment
- Time to research coordinator outreach event
- Number of research coordinator outreach event
- Automated phone or text message reminder trends (e.g. number of reminders required)

Post Enrollment Events

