Patients in both the treatment and control arms will receive an identical overview regarding the proposed intervention and randomization will only occur after the consent process has been completed. Patients in the control arm will receive usual care and can continue using their existing pharmacy. Patients in the treatment group will begin receiving their medications in pre-filled medication trays from Friendship Pharmacy. Patients will receive 5 trays on a monthly basis in order to accommodate a 30-day, insurance-reimbursed fill schedule.

As much as possible our group will attempt to collect data as part of usual clinical practice. For example, we will attempt to consent patients with upcoming clinic visits who meet enrollment criteria on the same day as their existing appointment. For patients whose appointment schedule does not permit us to do so we'll look to schedule a research visit on a day and time that is most convenient.

We will also attempt to utilize existing laboratory tests so as to not duplicate services. Given the present study assesses patient adherence for hypoglycemic medications, we would like to have an HbA1c measure for each patient at the onset and conclusion of the study. Rather than simply re-order this test we have set a 45 day window such that if an A1C was ordered as part of usual care in the 45 days before the patient's study start date or end date we will abstract that value from the patients chart for use in our analysis.

As clinical guidelines recommend that patients with poorly controlled glycaemia have an A1C taken quarterly, we reserve the right to request an A1C for patients who have not had one as part of usual care. If none of the conditions previously described are met we will order an A1C under the research protocol, thereby incurring a research expense on behalf of the patient.

LDL, HDL triglycerides, and total cholesterol levels are also of interest to our group in instances where the patient has both diabetes and hyperlipidemia. As a lipid panel is typically ordered once a year for patients with hyperlipidemia our group has set a 3 month window from the study start and end date. If the patient's lipid panel was drawn as part of usual care during this 3-month time window we will abstract the value from the patient's chart. Below is a summary of the information we will collect at the two visits common to all patients participating in the study.

Induction Visit

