Patients will be consented by a trained research coordinator and have the following information collected from them:

- Electronic mailing address and phone number
- Blood pressure-once at the beginning and once at the end of the visit
- Demographic survey
- Montreal Cognitive Assessment (MoCA exam)- a screen for cognitive impairment
- Cumulative Illness Rating Scale (CIRS)- a measure of comorbid illness burden
- Short Form 12 (SF-12)- a measure of general quality of life
- Brief Medication Question (BMQ)- a self reported assessment of medication adherence and medication adherence related factors (e.g. cost burden of drugs)

Concluding Visit

Patients will return their connected pillbox and have the following information collected from them:

- Blood pressure- once at the beginning and once at the end of the visit
- HbA1c test and lipid panel if data cannot be abstracted from the chart
- Patient satisfaction and attitudes toward adherence system

The care coordinator will also assist the patient in transitioning from the tray to another method of receiving their medications. Patients will have the option of either remaining with Friendship Pharmacy or be transferred back to their original pharmacy.

Methods

Measuring Adherence

Proportion of Days Covered (PDC) is the metric currently used by CMS and NCQA to assess patient medication adherence; the metric is calculated using pharmacy benefit data. The present study utilizes an interval-based PDC calculation defined as medication possession during the interval from the index date (the patient's study start date) to the end of the period being assessed (the patient's end date). In this way, the number of days of medication supplied throughout the period becomes the numerator and is divided by the number of days in the overall period itself. Intervals during which patients are hospitalized or in hospice are excluded from the PDC calculation

As PDC is an assessment of medication adherence for a single drug the calculation must be modified for patients taking multiple medications. Of interest in this study is patient adherence to oral hypoglycemic drugs. Our group recognizes the following categories as oral hypoglycemic agents: sulfonylurea, metformin hydrochloride, glitazones, acarbose, and meglitinides.

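### LOCF extended to HbA1c gives a change of exactly zero to any leaver with no HbA1c after study start, and the plan does not say whether routine chart values may be carried forward instead

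*Combined protocol and SAP*

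**What the plan says.** The Statistical Analysis section compares change scores by an unpaired t test under intention to treat. Patients who die or withdraw "will be analyzed by the imputation method of last observation carried forward, using the medication adherence level of the time available". The next sentence reads "A similar methodology will be used for the secondary (exploratory) endpoints of diabetes control and re-admission rate". No other missing-data rule for HbA1c appears in the document.

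On when HbA1c is measured, Post Enrollment Events says "we would like to have an HbA1c measure for each patient at the onset and conclusion of the study". If a test was ordered in usual care "in the 45 days before the patient's study start date or end date we will abstract that value"; otherwise the study may order one. The Concluding Visit list includes "HbA1c test and lipid panel if data cannot be abstracted from the chart". Only two visits are described, and no interim HbA1c is scheduled.

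The endpoint list, however, describes HbA1c as "generally collected every three months as part of routine clinical care for diabetic patients with HbA1C over 7.5", so mid-study values may well sit in the chart. The plan does not say whether such a value can serve as the last observation. It also does not say what the end date is for a patient who withdraws.

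**The concern.** For adherence, LOCF carries forward a level observed during the study, because claims accumulate up to withdrawal. HbA1c has no scheduled equivalent. If the last HbA1c held is the baseline one, LOCF becomes baseline carried forward and the change is zero by construction.

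Zero is not a neutral value. Entry requires a last charted HbA1c of at least 7.5, so some average fall in both arms is plausible from selection alone. The zeros then do three things:

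- They dilute any real difference.
- They reduce the SD that enters the t test.
- They add a bias if the arms lose patients at different rates.

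Unequal loss is plausible here. The Compensation section allows disenrolment when the cost gap at the new pharmacy is too large and the patient does not accept it. Control patients keep their existing pharmacy, so this exit exists only in the treatment arm.

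**Working it through.** **The plan's own figure.** Inputs from Target Population: difference 15, SD 30, two-sided 5%, 80% power, 15% drop-out. n = 2 × (1.960 + 0.842)² × (30/15)² = 62.8, so 63 per arm; 63 / 0.85 = 74.1, so 75. The stated size reproduces. It concerns adherence; no figure is given for HbA1c.

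**Leavers.** 0.15 × 75 = 11.25 per arm, about 22 of 150.

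**Share of leavers scored zero, by reading.** Readings (b) and (c) assume leaving times uniform over 182 days, a routine test every 91 days, and a baseline test drawn u = 0 to 45 days before start.

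- (a) Only the onset and conclusion values count: 100% of leavers without an end value, up to 11.25 per arm.
- (b) The end date is the withdrawal date and the 45-day look-back applies. A post-start value qualifies on 45 + u of the 182 days, so the share at zero is (137 − u)/182: 75% at u = 0, 51% at u = 45, mean 63%.
- (c) Any post-start chart value may be carried forward. The first falls on day 91 − u, so the share at zero is (91 − u)/182: 50% at u = 0, 25% at u = 45, mean 38%. That is 2.8 to 5.6 patients per arm.

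**Dilution with equal drop-out.** Factor = 1 − drop-out × share at zero, assuming leavers would otherwise have had the completers' mean change and that any carried post-start value equals it.

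- (a) 1 − 0.15 × 1 = 0.85; a difference of 0.50 becomes 0.425.
- (c) 1 − 0.15 × 0.50 = 0.925 to 1 − 0.15 × 0.25 = 0.9625.

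**Unequal drop-out.** Assumed: 20% treatment v 10% control, a common fall of 0.5 points, all leavers set to zero.

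- No true effect: 0.80 × (−0.5) − 0.90 × (−0.5) = −0.40 + 0.45 = +0.05, in favour of control.
- True effect 0.50: 0.80 × (−1.0) − 0.90 × (−0.5) = −0.80 + 0.45 = −0.35.
- The null shift scales with the assumptions: 0.03 for a common fall of 0.3, 0.10 for a fall of 1.0, and 0.10 for a fall of 0.5 with 25% v 5% drop-out.

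**SD.** With an assumed SD of 1.30 and 15% zeros, variance = 0.85 × (1.30² + mean²) − (0.85 × mean)².

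- Control, mean −0.5: 0.85 × 1.94 − 0.181 = 1.468, SD 1.21.
- Treatment, mean −1.0: 0.85 × 2.69 − 0.7225 = 1.564, SD 1.25.

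**The case against.** A reader might infer that HbA1c is measured only at start and end, and hence that most leavers are scored zero. The documents do not support that. They describe routine three-monthly testing, note that guidelines recommend quarterly tests, and let the study request one. Two values are scheduled; more may exist. The share at zero runs from about 25% to 100% according to rules the plan leaves unwritten, and it is below half on average under reading (c).

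A reader might also infer that the 45-day look-back by itself lets one chart value serve as both baseline and end value for leavers generally. That overlap can arise only for those leaving within 45 days, about a quarter of leavers if leaving is uniform (45/182), and only if the end date means the withdrawal date.

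Other points for the plan have weight. The extension sentence is loose and could refer to the change score, the t test or intention to treat as well as LOCF, although LOCF is the sentence directly before it. Treatment-arm leavers may lose the trays and reminders, so the completers' benefit may overstate what they would have had, and the dilution would then be smaller. The analysis baseline may be a fresh test rather than the eligibility value, which weakens the selection-driven fall.

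The effect on inference is also modest. With equal drop-out the test statistic is about 0.425 / 0.201 = 2.1, where 0.201 = √((1.468 + 1.564)/75). In 64 completers per arm it is about 0.50 / 0.230 = 2.2. The null shift of 0.05 is about a quarter of its standard error of 0.198.

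These points limit the size of the problem. They do not supply a rule for a leaver who has no HbA1c after study start.

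**Conclusion.** The point holds in a limited form. On the natural reading, the plan gives zero HbA1c change to every leaver without a post-start value, and it leaves open whether routine values can prevent this. That is up to about 11 of 75 per arm at the planned drop-out, or roughly a quarter to a half of leavers if routine values count under the assumed timings.

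The 15% shrinkage is the extreme for equal 15% drop-out. It requires that all leavers get zero and would otherwise have changed as completers did. The 0.05-point null shift rests on assumed drop-out rates and an assumed common fall. The document gives no HbA1c effect, SD or drop-out by arm.

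The stakes are bounded. HbA1c is exploratory, is to be analysed only if sample size allows, and is left to larger future studies for power. The adherence result and its sample size are unaffected. The correction is still worth making: improved blood glucose is a named exploratory aim, and the ability to measure HbA1c is one of the stated reasons for choosing this population.

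**What to change.** In Statistical Analysis, take HbA1c out of the LOCF sentence and state that:

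1. No value dated on or before study start may be used as the end value.
2. For leavers who permit chart use, the end value is the routine HbA1c closest to the planned 6-month date, counted from study start and not from withdrawal, within a stated window (for example 45 days either side).
3. The 6-month HbA1c is analysed on arm and baseline HbA1c. Values still missing are multiply imputed, using interim routine results where available.
4. LOCF is kept only as a sensitivity analysis.

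Items 1 and 2 and the imputation in item 3 address the defect. Baseline adjustment is a suitable model for them and in line with the plan's own adjusted analysis of adherence.

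The cost is a few sentences, chart abstraction for about 22 patients, and slightly wider intervals. Visits, sample size and the primary analysis do not change.

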With consent from their physician, eligible patients will be sent an initial contact letter informing them of their eligibility to participate in the study. Approximately, 1-2 weeks later a research coordinator will call the patient and educate the patient on the study objectives, benefits, and risks. Patients may verbally confirm their participation in the study at this time, allowing the coordinator to prepare a connected pillbox for their upcoming appointment. Verbal confirmation is not considered formal consent, which will be obtained during the in-person, scheduled appointment. The initial contact letter will also notify the patients that they can decline the informational phone call and provide the patient an email/phone number to directly communicate this request.

At the scheduled appointment patients who have verbally confirmed their interest in participating will be approached to formally enroll in the study. This appointment may occur in the primary care clinic, endocrinology clinic, internal medicine clinic, in the Clinical and Translational Research Center (CTRC), or at the patient's home. All patients retain the right to not participate despite having verbally confirmed prior interest in enrolling.

Early Withdrawal of Subjects

Participants may be withdrawn from study participation without their consent if: 1) the PI feels it is best for their safety and/or health, 2) they have not followed the study instructions, or 3) the PI sponsor, or Office of Regulatory Affairs at the University of Pennsylvania decide to stop the study.

Participants also have the right to drop out of the research study at anytime. If a participant wishes to withdraw from the research study he or she need only notify the study coordinator. Participants will be able to keep any compensation for study activities they have participated in, however, they will not receive compensation for study activities they have not participated in. All participants will be made aware of withdrawal procedures when informed consent is obtained.

Vulnerable Populations

Children, pregnant women, neonates, or prisoners are not included in this research study. Economically or educationally disadvantaged persons may participate in this study. We will minimize the risk of coercion by making clear in the consent process that participation in the study is voluntary and separate from their medical care and that non-participation will not affect how they are treated clinically.

Study Design

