A pharmacist at Friendship Pharmacy will load a patient's complete medication schedule and seal each medication tray using a heat-sealing system that uses compressed air. The system will seal each individual medication compartment in order to minimize drug waste in instances when the patient drops the pillbox or tray. Each medication compartment will be labeled with all the drug names and respective doses housed within it for quality and safety purposes. Complete printed labels identical to those found on the exterior usual care medication vials will accompany the trays in order to comply with Pennsylvania state pharmacy regulations. PRN (e.g. opioids) and frequently titratable medications (e.g. warfarin, tacrolimus) will not be included in the tray and will be provided to the patient in usual care medication vials.

Friendship Pharmacy will refill medication trays on a monthly basis only at patient request. An automated reminder will be initiated 10 days prior to the patients refill date. Failure to refill will be followed up by a personalized call from Friendship Pharmacy 7 days prior to the patients expected refill date. Refill reminders will continue every 3 days after initial outreach until patients initiate a tray refill.

Connected Pillbox

After consenting to participate in the study patients will receive a connected pillbox that has been activated for use on the Verizon Wireless network. Using embedded sensors, the pillbox senses volume changes within individual compartments and sends this raw, encrypted data to a dedicated server in the cloud. TowerView's algorithms process capacitance data and determine whether a patient took his or her medications. In instances when patients did not take their medications, TowerView can send the patient an automated text message, phone call, or email reminder. For patients who prefer not to receive such notifications the pillbox comes equipped with visual (flashing blue light) and audio (loud beeping) reminders as well.

Initial notification schedules will be assigned based on patient preference by the research coordinator (ex: 9AM, 3PM, 9PM). Using TowerView's web based software, however, patients can alter their notification

schedule at any time; furthermore, notifications can be set for medications that do not reside within the pre-filled trays. This feature has been added to accommodate PRN, frequently titratable and injectable medications that are unable to be included as part of the tray.

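### Withdrawal for not following study instructions lets the study cut follow-up short, mainly in the treatment arm, for behaviour related to the adherence outcome

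*Combined protocol and SAP*

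**What the plan says.** Early Withdrawal of Subjects gives three grounds for removal by the study. It opens: "Participants may be withdrawn from study participation without their consent if: 1) the PI feels it is best for their safety and/or health". The second ground is that "they have not followed the study instructions", and the third is a decision to stop the study. The section does not define study instructions and does not separate stopping the device from leaving the study.

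Statistical Analysis says: "For the primary endpoint, analyses will be performed according to the intention-to-treat principle". It adds that those who die or withdraw before the end "will be analyzed by the imputation method of last observation carried forward, using the medication adherence level of the time available". Change scores in PDC "will be compared using unpaired t tests".

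The arms differ in what they are asked to do:
- **Treatment.** Prescriptions move to a single pharmacy, and "Friendship Pharmacy will refill medication trays on a monthly basis only at patient request". The pillbox feeds a dashboard on which the coordinator sees adherence (Research Coordinator Outreach).
- **Control.** "Patients in the control arm will receive usual care and can continue using their existing pharmacy".

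Measuring Adherence takes PDC from pharmacy benefit data, from the patient's start date to the patient's end date. The Compensation section adds a second way out of the study: disenrolment where the cost difference after the pharmacy transfer is too large to make up and the patient does not accept it.

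**The concern.** In an adherence trial, failing to follow instructions can lie close to the outcome. A treatment patient who stops requesting trays, and fills nowhere else, departs from the intervention and lowers PDC by the same act. Every participant is selected for PDC below 80%, so this behaviour is foreseeable. Controls have no device, trays or dashboard, so the ground has much less to act on in their arm. The research team that would apply it knows the allocation.

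If the study ends follow-up for such a patient, PDC is scored over a shorter window than for everyone else. Intention to treat keeps the patient in the arm by name, but the outcome is no longer the six-month outcome, and the shortening results from behaviour after randomisation. The concluding-visit blood pressure and survey may also be lost, and HbA1c where the chart has none.

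**Working it through.** **The plan's own figure.** Inputs from Target Population and Statistical Analysis: difference 15 points, SD 30, two-sided 0.05, 80% power, 15% dropout.

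n per arm = 2 × (1.960 + 0.842)² × 30² / 15² = 62.8, so 63. Then 63 / 0.85 = 74.1, so 75. The stated 75 per arm reproduces. The 15% dropout is not split by arm or cause.

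**Assumptions not in the documents.** Six months is 180 days. A treatment patient takes one 30-day fill and is withdrawn on day w. LOCF uses PDC up to w, which is how I read the time-available wording together with the start-to-end-date definition of PDC. Between 5% and 10% of the treatment arm (about 4 to 8 of 75) is withdrawn this way, and no controls are. Baseline PDC is unaffected, so an error in post-baseline PDC passes in full into the change score.

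**Formulas.** Carried-forward PDC = 30 / w. Patient-level bias = carried-forward PDC minus 180-day PDC. Arm-level bias = fraction withdrawn × patient-level bias.

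*No further fills: 180-day PDC = 30 / 180 = 16.7%*

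| Day w | Carried forward | Patient bias | Arm bias at 5% | Arm bias at 10% |
|---|---|---|---|---|
| 45 | 66.7% | +50.0 | +2.5 | +5.0 |
| 60 | 50.0% | +33.3 | +1.7 | +3.3 |
| 90 | 33.3% | +16.7 | +0.8 | +1.7 |

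*Half the remaining days covered: 180-day PDC = (30 + 0.5 × (180 − w)) / 180*

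| Day w | Carried forward | 180-day PDC | Patient bias |
|---|---|---|---|
| 45 | 66.7% | 54.2% | +12.5 |
| 60 | 50.0% | 50.0% | 0 |
| 90 | 33.3% | 41.7% | −8.3 |

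In this second case the arm-level bias at 5-10% withdrawn is +0.6 to +1.25 points (day 45), 0 (day 60) or −0.4 to −0.8 (day 90).

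**Effect on the test.** With no true effect and 75 per arm, SE = 30 × √(2/75) = 4.90. The two-sided rejection rate is Φ(b/SE − 1.96) + Φ(−b/SE − 1.96), where b is the arm-level bias. With no further fills, withdrawal at day 60 of 5% or 10% of the arm moves the nominal 5% to about 6% or 10%. Withdrawal at day 45 moves it to about 8% or 18%.

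**The case against.** The strongest objection is that the plan already deals with these patients. LOCF keeps them in the t test in their randomised arm. A reader might infer that the rule removes non-adherers from the analysis, or that it flatly contradicts intention to treat. The documents do not support either. Deleting the lowest 4 or 8 change scores of 75 from one arm would give a bias of about 3.3 or 6.1 points, but nothing in the plan prescribes deletion. This part of the objection stands, and the harm is confined to truncated follow-up.

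Second, no section says that poor adherence leads to withdrawal. Missed doses trigger coordinator outreach, missed refills trigger repeated reminders, and an unanswered reminder is accepted. Day 45 may also be early: the plan's own discontinuation threshold is more than 30 days without a refill, which runs past day 60 if counted from the end of supply. This stands as a limit on how often the ground would be used. It does not limit what the undefined ground permits.

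Third, a reader might infer that the ground serves no safety purpose, or that controls have nothing to follow. The Risks section asks patients to bring all medications for reconciliation and to report hypoglycaemia, and parts of that wording are not confined to one arm. Neither inference holds.

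Fourth, a reader might infer that the bias must favour the intervention. The second table shows otherwise.

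Finally, the same truncation affects voluntary drop-out and the cost-related disenrolment, so amending the second ground alone would leave the mechanism in place. That is right, and the fix has to cover the analysis as well. The lost visit data concern exploratory endpoints only.

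**Conclusion.** The concern holds in limited form. The study can end follow-up on a discretionary, undefined ground that overlaps with the outcome and bears mainly on one arm. The plan does not say that claims PDC is collected to month six afterwards, although claims data do not depend on device use. That weakens the intention-to-treat comparison.

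For patients who stop filling altogether and are withdrawn at day 45 to 60, with 5-10% of the treatment arm affected, the arm mean is inflated by about 1.7 to 5 points, against a hypothesised 15. Later withdrawal reduces this, and partial refilling can bring it to zero or reverse it. The fill pattern, withdrawal day, withdrawn fraction and one-arm pattern are all assumed. The documents give no withdrawal rates by arm, so the greater exposure of the treatment arm is an inference from the design. The direction of bias is not certain, but the exposure is foreseeable and avoidable at almost no cost.

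**What to change.** - **Early Withdrawal of Subjects.** State that not using the pillbox, trays or reminders, or not ordering refills, is not by itself a reason for withdrawal from the study. Such a patient may stop the device and stay in follow-up. Define what study instructions then covers. The safety and study-stopping grounds are untouched.
- **Statistical Analysis.** State that claims-based PDC over the full six months is used, in the randomised arm, for every randomised patient. This includes those who leave the intervention and those disenrolled over cost under Compensation. The exceptions are withdrawal of consent for data use and end of insurance coverage. LOCF then applies only where claims are truly unavailable, or as a sensitivity analysis.
- **Follow-up and reporting.** Invite these patients to the concluding visit, and report withdrawals by arm and reason.

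The cost is a small protocol and consent amendment, and an effect estimate that may be slightly less favourable. The planned 75 per arm does not change.
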